5.2 Radiation Administration

5.2.1 Treatment Volume Parameters

The ICRU 50 recommended terminology will be used to define the radiation treatment parameters. The definitions of clinical tumor volume (CTV) will vary according to the tumor location, stage of disease, response to pre-radiation therapy, and histology.

The GTV corresponds to the gross tumor. This study does not include tumors with gross disease.

The CTV corresponds to the area that is likely to be microscopically involved with tumor.

All patients must have target volumes (chest wall and regional lymphatics) contoured. All contours should be performed according to Radiation Therapy Oncology Group (RTOG) guidelines. These guidelines are available online at <http://www.rtog.org/atlas/breastCancer/main.html>. In addition, the left ventricle and region of the left anterior descending artery will be contoured.

An additional margin to account for penumbra is to be determined for specific beam parameters at the Francis H. Burr cyclotron. The additional margin needed to account for penumbra depends on the depth of the tumor in the tissue being treated, size of the field, and field arrangement.

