1.2 Primary Objectives

1.2.1 To determine the feasibility of using proton radiation for the treatment of invasive breast cancer following surgery (mastectomy or breast-conserving) based on the occurrence of grade 3 or higher radiation pneumonitis or any grade 4 toxicity within 3 months after the completion of radiation treatment. The goal is to enable women with breast reconstruction to undergo radiation therapy without removal or manipulation of reconstruction in order to allow radiation delivery without excessive pulmonary and cardiac dose and to enable patients with unfavorable cardiac anatomy (as defined by $\geq 5\%$ of the heart receives ≥ 20 Gy and/or LAD receives ≥ 20 Gy with conventional planning) to undergo chest wall irradiation with better cardiac sparing.

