Symptomatic radiation pneumonitis is a sub-acute side effect of radiation for treatments involving lung tissue.³⁶ When irradiating the chest wall and regional lymphatics, 20-30% ipsilateral lung may receive radiation to a dose of 20 Gy. With implants in place, this dose may be even higher and this is one reason why it may be recommended that implants be removed or reconstruction be delayed. In addition, recent literature for patients being treated for lung cancer report the importance of large volumes of lung receive low dose irradiation (5 Gy or 10 Gy).¹² Although the meaning of this for patients with breast cancer is less clear, it is important to note the techniques using electron radiation and/or some IMRT techniques generally decrease the volume of lung receiving 20 Gy, but increase the volume of lung receiving lower doses of radiation. Protons are capable of reducing both high and low doses of radiation to the lung. (Figure 3). Radiation pneumonitis is reported in approximately 1-5% of patients treated for breast cancer without concurrent chemotherapy.^{33, 37-38} However, the risk of radiation pneumonitis has been shown to increase with treatment of the regional lymph nodes and/or concurrent chemotherapy and rates as high as 20% have been reported in patients treated with concurrent paclitaxel and radiation.³⁹⁻⁴¹ Radiation pneumonitis generally resolves without treatment, but may require hospitalization or a course of steroids. The incidence of RP as reported by several recent series that utilized both modern chemotherapy and radiation therapy techniques are summarized below. The majority of these reports have used the Radiation Therapy Oncology Group (RTOG) acute lung morbidity scoring system to describe the severity of RP:

CONFIDENTIAL

This document is confidential. Do not disclose or use except as authorized.

	Grade 0	Grade 1	Grade 2	Grade 3	Grade 4	Grade 5
RTOG ACUTE LUNG MORBIDITY SCORING CRITERIA	No Change	Mild symptoms of dry cough or dyspnea on exertion	Persistent cough requiring narcotic, antitussive agents/dyspnea with minimal exertion	Severe cough, no response to narcotic antitussives or dyspnea at rest/clinical or radiological evidence of acute pneumonitis/intermittent O ₂ or steroids may be required	Respiratory insufficiency/continuous oxygen or assisted ventilation	Fatal

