5.2.4 Dose Specification and Schedule

The dose prescribed to the chest wall should be 45-50.4 Gy(RBE) to the chest wall and 45-50.4 Gy(RBE) to the regional lymphatics. Ninety-five percent of the target volume should receive 45-50.4 Gy(RBE) at the discretion of the physician. The chest wall incision may receive an additional 10 Gy with electron radiation at the discretion of the treating physician, but incision boost is not required. Questions regarding dose fractionation should be discussed by contacting [REDACTED]

CONFIDENTIAL

This document is confidential. Do not disclose or use except as authorized.

Treatments will be typically administered once per day, 5 days per week. Doses will be prescribed to the appropriate isodose line encompassing the CTV such that the gradient within a volume is +7% to -5%. Dose will be reported in Gy(RBE), Gray Radiobiological Equivalent (where 1 Gy(RBE)= proton dose Gy x RBE [radiobiological effective dose], RBE = 1.1). A RBE of 1.1 has been selected for protons and is based on RBE determinations in animal and cell culture systems.⁸

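### The goal of avoiding excessive pulmonary dose has no planned measure: the lungs are not named for contouring and no lung-dose summary is planned

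*Combined protocol and SAP*

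**What the plan says.** Section 1.2.1 defines feasibility "based on the occurrence of grade 3 or higher radiation pneumonitis or any grade 4 toxicity within 3 months after the completion of radiation treatment". Its next sentence states the goal, which for women with breast reconstruction includes "radiation delivery without excessive pulmonary and cardiac dose".

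Section 5.2.1 sets out the contours. For the targets: "All patients must have target volumes (chest wall and regional lymphatics) contoured". For method: "All contours should be performed according to Radiation Therapy Oncology Group (RTOG) guidelines". For organs at risk: "In addition, the left ventricle and region of the left anterior descending artery will be contoured". The lungs are not named, and neither is the whole heart.

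Section 5.2.4 fixes the unit for reporting dose ("Dose will be reported in Gy(RBE), Gray Radiobiological Equivalent") but asks for no organ dose. Lung dose is discussed only in the background. Section 2.2 says that with chest wall and nodal treatment "20-30% ipsilateral lung may receive radiation to a dose of 20 Gy", and that the figure may be higher with implants in place. It also refers to lung cancer literature on volumes receiving 5 or 10 Gy, says that its meaning in breast cancer is less clear, and states that protons can lower both high and low lung dose.

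**The concern.** The cardiac half of the stated goal has planned measurements: two named contours, strain echocardiography at three time points and cardiac biomarkers. The pulmonary half has a clinical event but no exposure measure, although the background argues for protons partly through lung dose.

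This matters because lung exposure can differ between patients within the protocol. Two proton techniques are studied in three cohorts (Section 12). Photons may deliver up to 20% of the prescribed dose when the proton machine is down, and respiratory gating is optional (5.2.3). Concomitant chemotherapy is allowed (5.3), and Section 2.2 cites pneumonitis rates as high as 20% with concurrent paclitaxel. If a pneumonitis case occurs, the planned report will not show what lung dose that patient received or how it compares with the rest of the cohort. Section 1.1 says the trial is meant to form the basis for future studies, and a description of lung exposure by technique would be useful to them.

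**Working it through.** **1. The plan's own figures.** Section 12.1 stops a cohort at 2 or more events in the first 12 and otherwise declares feasibility at no more than 2 in 26. With event probability p:

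- P(stop early) = 1 − (1−p)^12 − 12p(1−p)^11. At p = 0.05: 1 − 0.5404 − 0.3413 = 0.118 (stated 12%).
- P(feasible) = P(X1=0)·P(X2≤2) + P(X1=1)·P(X2≤1), with X1 ~ Bin(12, p) and X2 ~ Bin(14, p). At p = 0.05: 0.5404 × 0.9700 + 0.3413 × 0.8470 = 0.813 (stated 81%). At p = 0.15: 0.1422 × 0.6479 + 0.3012 × 0.3567 = 0.200 (stated 20%).

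All three reproduce. With the limit of no more than 3 in 26 given in Section 6.3, the acceptance probabilities become 86.9% and 31.7%, so the stated 81% and 20% match only the limit in 12.1.

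**2. Where a lung dose could enter the plan.**

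- 1.3 (secondary objectives): pneumonitis rate and severity; no lung dose.
- 5.2.1 (contours): targets, left ventricle, LAD region.
- 5.2.4 (dose): prescription, target coverage, unit; no organ metric.
- 5.2.5 (quality assurance): dose verification by a physicist; no lung dose-volume item.
- 7 (calendar): none.
- 12.1 (primary analysis): event counts only.
- 12.2 (secondary analyses): toxicity rates, progression-free survival, strain echocardiography. The only mention of dose is an optional dose-level effect in the echocardiography model, which is not a lung dose.

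**3. What the event count says about the lung.** Exact (Clopper-Pearson) 95% intervals, ignoring the interim look:

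- 0/26: 0 to 13.2%
- 1/26: 0.1 to 19.6%
- 2/26: 0.9 to 25.1%

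Grade 3 rates in the summary table of Section 2.2 run from 0% to 12%, so every passing result is compatible with nearly all of that range. The count also includes any grade 4 toxicity, so the events need not be pneumonitis.

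**4. What a lung-dose summary would give.** The half-width of a 95% interval for a mean is t(0.975, n−1) × SD / √n. For n = 26 this is 0.404 SD; for n = 32 (96 patients over three cohorts) it is 0.361 SD. The documents give no SD for V20, the percentage of ipsilateral lung receiving at least 20 Gy. For assumed SDs of 3, 5 and 8 percentage points and n = 26:

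- 0.404 × 3 = 1.2 points
- 0.404 × 5 = 2.0 points
- 0.404 × 8 = 3.2 points

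These widths cannot be compared with the intervals in step 3, because one is for an event rate and the other for a mean exposure. They show only that a cohort of this size can describe lung exposure usefully.

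**The case against.** The contour list in 5.2.1 is probably not exhaustive. The whole heart is also unnamed, yet eligibility without reconstruction (3.1.2) depends in part on the share of the heart receiving at least 20 Gy, which needs a heart contour. The sentence on the left ventricle and LAD region may simply add cardiac substructures to routine contours. The RTOG guidelines may cover the lung, but their content is not in the documents. A reader might infer that the lungs will go uncontoured, or that the trial cannot show its lung exposure. The documents do not support that: a planning CT is obtained (5.2.3), and lung values could be extracted later. Nor can one say that no form records lung dose, because the fields of the Treatment Form are not shown.

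It is also fair to say that the sentence on pulmonary and cardiac dose is a goal, while feasibility is defined by toxicity. The background treats the dosimetric advantage as supported by planning studies and calls for clinical outcomes. Judging a pilot on clinical events is legitimate, and the rule has stated operating characteristics that reproduce. A lung-dose table would not make a result of 0 to 2 events in 26 any more precise. With few pneumonitis cases, it could not separate lung exposure from chemotherapy as a cause.

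All of this stands. It limits the point to something not prespecified. It does not supply the missing measure: even if lungs are contoured and doses stored, no objective or analysis in the available text uses them.

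**Conclusion.** The concern holds as a modest gap in data collection and reporting. One part of the goal in 1.2.1 has no planned measure in the available text, so the planned report will not describe lung exposure for 3D conformal protons or IMPT, or place it beside any pneumonitis cases. No sample size, decision rule or stated probability is wrong on this account.

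Two stronger inferences are not supported. The first is that the feasibility verdict is invalid without lung dose: the verdict is defined by toxicity and would rest on the same counts either way. The second is that the 20–30% figure in Section 2.2 is a benchmark the trial could formally test against. It is a loose statement about conventional treatment, said to be possibly higher with implants, while the trial enrols patients with reconstruction, with unfavorable cardiac anatomy and with intact breasts.

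The precision of 1.2 to 3.2 points depends entirely on the assumed SDs of 3 to 8 points; only the multiplier of 0.40 SD follows from the design.

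**What to change.** - In 5.2.1, name both lungs among the structures to be contoured.
- In 12.2, add a descriptive summary by cohort of ipsilateral-lung V20 (mean with 95% confidence interval) from the delivered plan, including any photon fractions. Report V10 and V5 as exploratory, because Section 2.2 itself calls the meaning of low-dose volumes in breast cancer less clear.
- List the lung dose of each pneumonitis case by grade, beside the cohort summary.
- Cite the 20–30% figure only as loose context, not as a formal comparator.

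The cost is routine contours on the existing planning CT, a few values from plans already made, and one extra table. No visit or procedure is added and no dose limit is proposed. The feasibility rule, sample size and operating characteristics do not change.

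Separately, the final limits of no more than 2 of 26 (Section 12.1) and no more than 3 of 26 (Section 6.3) must be reconciled, so that the protocol states one rule and the probabilities that belong to it.

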5.2.2 Timing of the radiation therapy

CONFIDENTIAL

This document is confidential. Do not disclose or use except as authorized.

Radiation therapy should be initiated no later than 20 weeks following chemotherapy and surgery. Surgery can exceed 20 weeks if the patient undergoes chemotherapy following surgery. Radiation should not be started earlier than 3 weeks following Taxane based chemotherapy.

5.2.3 Patient Simulation

Patient set-up and immobilization will be determined prior to obtaining the planning CT scan. The type of immobilization will be determined by the treating physician, but treatment should be delivered in the supine position.

Patient set-up reproducibility is critical for both conventional radiotherapy and proton radiotherapy and the use of daily imaging with diagnostic quality imaging will be performed. For photon therapy, it is most common to perform weekly portal images that are not always of diagnostic quality.

Respiratory gating is allowed, but not required. The decision to use this technique will be at the discretion of the treating radiation oncologist. Proton radiation should be less sensitive to breathing motion as it is delivered with en face fields rather than tangent fields.

To avoid treatment delays resulting from the machine being down, photon beam radiation can be administered. The maximum dose delivered by photons will be 20% of the prescribed dose. Treatment delays will be allowed if a serious adverse event occurs due to protocol therapy. Treatment delays will also be allowed for patients who experience a serious adverse event not related to protocol therapy (e.g. concurrent chemotherapy requiring hospitalization for neutropenia).

5.2.4 Dose Specification and Schedule

The dose prescribed to the chest wall should be 45-50.4 Gy(RBE) to the chest wall and 45-50.4 Gy(RBE) to the regional lymphatics. Ninety-five percent of the target volume should receive 45-50.4 Gy(RBE) at the discretion of the physician. The chest wall incision may receive an additional 10 Gy with electron radiation at the discretion of the treating physician, but incision boost is not required. Questions regarding dose fractionation should be discussed by contacting [REDACTED]

CONFIDENTIAL

This document is confidential. Do not disclose or use except as authorized.

Treatments will be typically administered once per day, 5 days per week. Doses will be prescribed to the appropriate isodose line encompassing the CTV such that the gradient within a volume is +7% to -5%. Dose will be reported in Gy(RBE), Gray Radiobiological Equivalent (where 1 Gy(RBE)= proton dose Gy x RBE [radiobiological effective dose], RBE = 1.1). A RBE of 1.1 has been selected for protons and is based on RBE determinations in animal and cell culture systems.⁸

5.2.5 Proton Radiation Parameters and Quality Assurance

The FHBPTC cyclotron produces a 230 MeV proton beam. The energy can be degraded to an appropriate energy to treat the desired depth. For treatment, intensity modulation of the proton beam may also be used for shaping of the beam and conformation to the target volume. Apertures and Lucite compensators may be used for shaping of protons and to conform to the distal aspect of the target volume.

Pre-treatment port films should be compared with a digitally reconstructed radiography (DRR) from the treatment planning system. Film or digital images will be taken prior to each treatment in accordance with the proton center's standard practice for all patients. These images are used to verify the position of the patient and the aperture. These digital images are permanently stored electronically for each patient. A physicist will perform dose verification for all treatment plans/fields.

5.3 General Concomitant Medication and Supportive Care Guidelines

Concomitant chemotherapy as dictated by protocol or the treating physician is allowed. All appropriate non-investigational supportive care medications or treatments may be used for optimal symptom management.

5.4 Duration of Therapy

Duration of therapy will be defined by protocol or dictated at the discretion of the treating physician.

Duration of therapy will depend on individual response, evidence of disease progression and tolerance. In the absence of treatment delays due to adverse events, treatment may continue as planned until finish or until one of the following criteria applies:

- Disease progression,
- Intercurrent illness that prevents further administration of treatment,

CONFIDENTIAL

This document is confidential. Do not disclose or use except as authorized.

- Unacceptable adverse event(s),
- Participant decides to withdraw from the study, or
- General or specific changes in the participant's condition render the participant unacceptable for further treatment in the opinion of the treating investigator.

5.5 Duration of Follow Up

Participants will be followed for at minimum 5 years after completion of study treatment or until death, whichever occurs first. Participants removed from study for unacceptable adverse events will be followed until resolution or stabilization of the adverse event.

5.6 Criteria for Removal from Study

Participants will be removed from study when any of the criteria listed in Section 5.5 applies. The reason for study removal and the date the participant was removed must be documented in the study-specific case report form (CRF). Alternative care options will be discussed with the participant.

In the event of unusual or life-threatening complications, participating investigators must immediately notify the Principal Investigator (or Protocol Chair), [REDACTED]

6. EXPECTED TOXICITIES AND DOSING DELAYS/DOSE MODIFICATIONS

The CTEP Active Version of the NCI Common Terminology Criteria for Adverse Events (CTCAE) will be utilized for AE reporting. The CTEP Active Version of the CTCAE is identified and located on the CTEP website at

http://ctep.cancer.gov/protocolDevelopment/electronic_applications/ctc.htm
<https://phsexchweb.partners.org/exchweb/bin/redir.asp?URL=http://ctep.cancer.gov/protocolDevelopment/electronic_applications/ctc.htm>. All appropriate treatment areas should have access to a copy of the CTEP Active Version of CTCAE. If possible, symptoms should be managed symptomatically. In the case of toxicity, appropriate medical treatment should be used.

All radiation related grade 2 and greater adverse events experienced by participants will be collected from the time of the start of radiation and throughout the study and until the final study visit. Participants continuing to experience toxicity at the off study visit may be contacted for additional assessments until the toxicity has resolved or is deemed irreversible.

It is anticipated that toxicities will be decreased with proton radiation.

CONFIDENTIAL

This document is confidential. Do not disclose or use except as authorized.

6.1 Possible Toxicities

Possible short-term side effects, during or shortly after radiation therapy. These are reversible.

- ❑ skin: redness, tanning, irritation (common); breakdown under breast or in armpit (variable)
- ❑ fatigue (variable)
- ❑ poor wound healing (variable)
- ❑ pneumonitis, with cough and fever (rare; occurs mostly in the first 3 months after radiation)
- ❑ radiation pericarditis (left breast only) (very rare)

Unlikely long-term side effects, many months or years after radiation therapy. These may not be reversible.

- ❑ skin changes (rare)
- ❑ rib fracture (rare)
- ❑ arm or hand swelling, influenced by additional surgery and chemotherapy (variable)
- ❑ shoulder stiffness, influenced by additional surgery (rare)
- ❑ arm weakness and/or numbness (brachial plexopathy) (very rare)
- ❑ secondary cancer many years from now (very rare)
- ❑ cardiac disease

6.2 Toxicity Management

All appropriate non-investigational supportive care medications or treatments (e.g. topical ointments, pain medications, etc.) may be used for optimal symptom management.

6.3 Dose Modifications/Delays

Doses of radiation used are considered standard, i.e., this is not a dose escalation study, and interruption of radiation is not anticipated. Delays or interruptions of radiation therapy will be at the discretion of the treating physician, but the primary investigator should be notified if the number of days exceeds 3. Dose modifications for side effects should not be made without informing the primary investigator.

Proton radiation for invasive breast carcinoma will be considered to be feasible following surgery (mastectomy or breast-conserving) if the rate of grade 3 or higher radiation pneumonitis within 3 months of treatment were no more than 5%, within the range associated with conventional techniques of adjuvant radiation. In addition to radiation pneumonitis, the feasibility of proton radiation will also be compromised by any grade 4 effect occurring within 3 months of treatment, skin toxicity and pericarditis. If 2 or more

CONFIDENTIAL

This document is confidential. Do not disclose or use except as authorized.

of the initial 12 patients were to experience grade 3 or higher radiation pneumonitis or any grade 4 toxicity within 3 months of finishing radiation, accrual will not continue further. The probability of stopping early is only 12% if the underlying rate of grade 3 or higher radiation pneumonitis or any grade 4 toxicity were truly 5%. Otherwise, the protocol will proceed to enroll a total of 26 patients and declare the feasibility of proton radiation if no more than 3 of them were to experience grade 3 or higher radiation pneumonitis or any grade 4 toxicity within 3 months after treatment.

CONFIDENTIAL

This document is confidential. Do not disclose or use except as authorized.

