12.1 Study Design/Endpoints

This is a pilot study substituting proton radiation for photon radiation, seeking to show the feasibility of proton radiation and to assess the rate of acute, sub-acute and late toxicities during and after proton radiation to the left chest wall and regional lymphatics. It is anticipated that patients undergoing proton radiation will not have increased toxicity compared to patients who have historically undergone photon radiation.

Proton radiation will be considered to be feasible as adjuvant treatment for invasive breast carcinoma in each cohort following surgery if the rate of grade 3 or higher radiation pneumonitis within 3 months of treatment were no more than 5%, within the range associated with conventional techniques of adjuvant radiation. In addition to radiation pneumonitis, the feasibility of proton radiation will also be compromised by any grade 4 effect occurring within 3 months of treatment, as well as skin toxicity and pericarditis. If 2 or more of the initial 12

CONFIDENTIAL

This document is confidential. Do not disclose or use except as authorized.

patients were to experience grade 3 or higher radiation pneumonitis or any grade 4 toxicity within 3 months of finishing radiation, accrual to a cohort will not continue further. The probability of stopping early is only 12% if the underlying rate of grade 3 or higher radiation pneumonitis or any grade 4 toxicity were truly 5%. Otherwise, the cohort will proceed to enroll a total of 26 patients and declare the feasibility of proton radiation if no more than 2 of them were to experience grade 3 or higher radiation pneumonitis or any grade 4 toxicity within 3 months after treatment. The two-stage design provides 81% power to accept that proton radiation is associated with a 5% rate of grade 3 or higher radiation pneumonitis or any grade 4 toxicity in a treated cohort. However, the probability is only 20% for declaring the feasibility of proton radiation if the underlying rate grade 3 or higher radiation pneumonitis or any grade 4 toxicity were truly 15%.

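### The primary feasibility cut-off is 3 events in 26 in Section 6.3 but 2 in 26 in Section 12.1; the Section 6.3 rule raises the chance of accepting a 15% toxicity rate from 20% to 32%

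*Combined protocol and SAP*

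**What the plan says.** Both sections describe a two-stage design for the primary endpoint, which is grade 3 or higher radiation pneumonitis or any grade 4 toxicity in the three months after radiation.

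- **First stage.** The two sections agree. Section 12.1 begins "If 2 or more of the initial 12" and Section 6.3 likewise counts how many "of the initial 12 patients were to experience grade 3 or higher radiation pneumonitis or any grade 4 toxicity within 3 months of finishing radiation". Two or more events end accrual.
- **Early-stop probability.** Both give 12% at a true rate of 5%. Section 12.1: "The probability of stopping early is only 12% if the underlying rate of grade 3 or higher radiation pneumonitis or any grade 4 toxicity".
- **Total.** Both give 26. In Section 12.1, "the cohort will proceed to enroll a total of 26 patients"; in Section 6.3 it is the protocol that goes on to 26.
- **Final cut-off.** The two sections differ. Section 6.3 would "declare the feasibility of proton radiation if no more than 3 of them were to experience grade 3 or higher radiation pneumonitis" or a grade 4 event. Section 12.1 would "declare the feasibility of proton radiation if no more than 2 of them were to experience grade 3 or higher radiation pneumonitis" or a grade 4 event.
- **Operating characteristics of the full design.** These appear only in Section 12.1: "The two-stage design provides 81% power to accept that proton radiation is associated with a 5% rate", and "the probability is only 20% for declaring the feasibility of proton radiation if the underlying rate" is in truth 15%.

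The opening of Section 12 plans 96 patients in three cohorts, with the proton techniques evaluated independently. Section 12.1.2 says endpoints will in general be analysed separately by cohort.

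**The concern.** These are two statements of one rule, not two rules: everything matches except the last number. Both stand in current text, and nothing in the protocol gives one section precedence.

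The rule decides the primary objective. Three events in 26 is an observed rate of 3/26 = 11.5%, and a cohort that ends there after passing the first stage would be declared feasible by a reader of Section 6.3 and not feasible by a reader of Section 12.1. While both cut-offs stand, the choice between them could be made after the event count is known.

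The unit also differs. Read literally, Section 6.3 applies one first-stage check to the first 12 patients on the protocol and ends at 26 patients overall. That would leave the second and third cohorts without a stopping rule of their own, and it does not fit a 96-patient, three-cohort study.

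**Working it through.** **Inputs** (Sections 6.3 and 12.1): first stage n₁ = 12, continue on 0 or 1 events; total n = 26, so 14 patients in the second stage; final cut-off r = 2 (Section 12.1) or r = 3 (Section 6.3); true rates p = 5% and 15% (Section 12.1). I add p = 10% as an intermediate value.

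**Formulas**

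- P(stop early) = 1 − P(X₁ = 0) − P(X₁ = 1), with X₁ ~ Bin(12, p).
- P(declare feasible) = P(X₁ = 0) × P(X₂ ≤ r) + P(X₁ = 1) × P(X₂ ≤ r − 1), with X₂ ~ Bin(14, p).

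**Components**

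| p | P(X₁=0) | P(X₁=1) | P(X₂≤1) | P(X₂≤2) | P(X₂≤3) |
|---|---|---|---|---|---|
| 5% | 0.5404 | 0.3413 | 0.8470 | 0.9699 | 0.9958 |
| 10% | 0.2824 | 0.3766 | 0.5846 | 0.8416 | 0.9559 |
| 15% | 0.1422 | 0.3012 | 0.3567 | 0.6479 | 0.8535 |

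**Step 1: reproduce the plan's figures with r = 2**

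- Early stop at 5%: 1 − 0.5404 − 0.3413 = 0.118 (stated 12%).
- Feasible at 5%: 0.5404 × 0.9699 + 0.3413 × 0.8470 = 0.813 (stated 81%).
- Feasible at 15%: 0.1422 × 0.6479 + 0.3012 × 0.3567 = 0.200 (stated 20%).

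All three reproduce. Ignoring the first-stage stop, P(Bin(26, 15%) ≤ 2) = 0.230, which does not match 20%. The stated figures therefore come from the two-stage calculation.

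**Step 2: the Section 6.3 cut-off, r = 3**

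- Feasible at 5%: 0.5404 × 0.9958 + 0.3413 × 0.9699 = 0.869.
- Feasible at 15%: 0.1422 × 0.8535 + 0.3012 × 0.6479 = 0.317.

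**Step 3: compare**

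| True rate | r = 2 | r = 3 | Difference |
|---|---|---|---|
| 5% | 81.3% | 86.9% | 5.6 points |
| 10% | 45.8% | 58.7% | 12.9 points |
| 15% | 20.0% | 31.7% | 11.7 points |

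At 15% the ratio is 0.3166 / 0.1996 = 1.59. The last column is also the probability that a cohort passes the first stage and finishes with exactly 3 events, the one outcome on which the two sections disagree. If three independent cohorts share the same true rate (an assumption), the chance that at least one lands there is 1 − (1 − d)³, with d the difference: about 16%, 34% and 31% at 5%, 10% and 15%.

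**The case against.** The strongest reply is that this is a pilot, that Section 12 is the statistical section, and that it alone gives the full operating characteristics. The intended cut-off can therefore be recovered. That is a good reason to believe 2 was meant, but the protocol nowhere says that Section 12 governs. Section 6.3 states the rule in full, in the section on toxicity, and already covers both mastectomy and breast-conserving surgery, so it is not plainly left over from a design limited to mastectomy.

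Three narrower points deserve weight:

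- No calculation in the plan is wrong. The fault is a contradiction between sections, and the computation serves to show which cut-off the stated figures belong to.
- The 2-versus-3 difference changes nothing during accrual, because the first-stage boundary is identical. It affects only the end-of-cohort declaration, and only when 0 or 1 of the 3 events fall in the first 12 patients.
- A team is unlikely to act on the protocol-level wording, since a total of 26 cannot fit a 96-patient study and Sections 12, 12.1 and 12.1.2 all work by cohort. This is a secondary wording conflict, though a real one.

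None of these removes the contradiction in the primary decision rule.

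**Conclusion.** The concern holds. Section 6.3 and Section 12.1 give incompatible cut-offs for the primary feasibility decision, and the stated 81% and 20% belong only to the cut-off of 2. Applied as written, Section 6.3 gives 87% and 32%, and it can reverse the conclusion for a cohort with exactly 3 events.

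The figures are exact binomial probabilities under the design as stated: 12 then 14 evaluable patients, independent outcomes, one common event rate within a cohort, and the first-stage stop enforced. Because it is the primary go/no-go rule, with nothing in the text to settle which version applies, it must be corrected despite the pilot setting.

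**What to change.** State the rule once. The cleanest change is to delete it from Section 6.3 and refer to Section 12.1. Alternatively, amend Section 6.3 to a cut-off of 2 and word both the stopping rule and the 26-patient total for each cohort. If the sponsor did intend 3, then Section 12.1 must change instead and report about 87% acceptance at a 5% rate and 32% at 15%.

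The cost is a short protocol amendment, with no change to sample size or data collection. One check should go with it. Section 12.1.1 says enrolment began in August 2011, and Section 12 says the accrual target was adjusted on observed data from mastectomy patients, so a cohort may already have been judged. The amendment should record which cut-off was applied to any such cohort, and whether its event count was known when the text was corrected. If a cut-off of 3 was used and the cohort had exactly 3 events, its conclusion would need to be revisited.
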